General safety data in this study include AEs, clinical safety laboratories, physical examinations (PEs), vital signs, and electrocardiograms (ECGs). The summarization of AEs will include only treatment-emergent AEs (TEAEs), defined as AEs that begin or worsen after randomization and ingestion of the first dose of randomized IMP. TEAEs and SAEs will be summarized by system organ class (SOC), severity, and relationship to IMP for each treatment group. Deaths, withdrawal from study treatment due to AEs, and withdrawal from the study due to AEs will each be summarized by treatment group.

Clinical safety laboratories, including hematology, blood chemistry, and urinalysis; PE findings; vital signs; ECG readings; and weight will be summarized by the value and by change from baseline in the value (where appropriate) at each postbaseline time point.

AESI:

All AESI will be identified and evaluated by routine safety monitoring of AEs and laboratory values (where appropriate) and will be summarized by severity and relationship to IMP for each treatment group

The following are considered AESI categories for this study:

- Hepatic Safety, including liver-associated enzymes, total bilirubin (TB), and any Hy's law cases ($\geq 3 \times$ ULN for either ALT or AST, with accompanying TB $> 2 \times$ ULN in the setting of no known other cause)
- Musculoskeletal Safety, including creatinine phosphokinase (CK)
- Diabetes and Glycemia, including new onset of diabetes and worsening of diabetes
- Hypoglycemia Associated with Metabolic Acidosis
- Renal Impairment, including lab measures of renal function
- Neurocognitive Events
- Atrial Fibrillation
- Tendon Rupture/Tendinopathy. The TRAC will adjudicate events of tendon rupture per the Tendon Rupture Independent Adjudicator Charter (TRIAC), and adjudicated events will be summarized.
- Malignancies

Additional postrandomization adjunctive lipid-modifying therapy:

The number and percent of patients in each treatment group requiring additional (postrandomization) adjunctive lipid-modifying therapy will be summarized by treatment and by lipid-lowering therapy class. The reasons for their additional treatment (hyperlipidemia versus hypertriglyceridemia) will be summarized. Medications will be summarized by treatment group.

TABLE OF CONTENTS

1.	TITLE PAGE.....	1
2.	SYNOPSIS	2
	TABLE OF CONTENTS.....	15
	LIST OF TABLES.....	20
3.	LIST OF ABBREVIATIONS AND DEFINITIONS OF TERMS.....	21
4.	INTRODUCTION	25

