The time to first occurrence of new onset of diabetes during the treatment period will be analyzed by a Cox model in the Prediabetes Efficacy Population. The date of new onset of diabetes will be the earliest date of the event observed during the treatment period. For this analysis, patients who are LTFU and discontinue the study drug early without experiencing a new onset of diabetes will be censored at 30 days after the last date of the treatment.

Secondary Efficacy Lipid and Other Biomarker Endpoints:

Percent change from baseline to Month 6 in LDL-C and change from baseline to Month 12 in HbA_{1C} will be analyzed using analysis of covariance (ANCOVA), with treatment group as a factor and the relevant baseline as a covariate. The ANCOVA for LDL-C will be performed using the FAS. The ANCOVA for HbA_{1C} will be performed in the Inadequately Controlled Diabetes Efficacy Population. Two methods for data handling will be used: the first (primary) will involve specification of the missing data mechanism using a pattern mixture model (PMM), while the second (supportive) will be observed case data only. For each analysis, the least squares mean (LSM) and standard error (SE) will be provided for each treatment group, along with the placebo-corrected LSM, its 95% CI, and associated p-value.

A nonparametric analysis based on Wilcoxon rank sum test and Hodges-Lehmann (H-L) estimate of location shift will be performed in the FAS for percent change from baseline to Month 6 in hs-CRP. No imputation will be performed for the hs-CRP endpoint due to the extreme skewed distribution.

Tertiary Lipid and Biomarker Endpoints:

Tertiary lipid and HbA_{1C}-related endpoints will be summarized and analyzed as needed. For each parameter at each time point, the value of the parameter, change and the percent change from baseline will be summarized by treatment group. The Mixed Model Repeated Measure (MMRM) analysis including factors of treatment group, time point (as a categorical variable), baseline value, and treatment group-by-time point interaction will be performed in the observed FAS data. The LSM and SE will be provided for each treatment group, along with the placebo-corrected LSM, its 95% CI, and associated p-value, as needed. A nonparametric analysis based on Wilcoxon rank sum test and H-L estimate of location shift will be performed in observed FAS data for percent change from baseline to Month 12 and end-of study in hs-CRP.

Safety Endpoints:

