10.6. Procedures and Schedule of Assessments

The study is comprised of 3 distinct periods: screening, run-in, and double-blind treatment.

The schedule of study events is provided in Appendix 1. However, a patient can be seen at any time for reasons of safety.

Note: If the patient discontinues IMP at any time after T1, please proceed to Section 10.7 for detailed instructions.

- If the patient agrees to clinical visits after withdrawing from IMP at any time after Visit T1, the visit will include all procedures and assessments except for those pertaining to IMP management (IMP dispensing, adherence, and accountability).
- If the patient agrees to telephone or other form of contact after withdrawing from IMP at any time after Visit T1, the contact will include collection of patient-reported information to complete the eCRF including concomitant medication use, AEs, SAEs, and potential clinical endpoints.
- Patient is expected to continue to receive IMP and complete study visits following a clinical endpoint unless, for some reason, this is no longer clinically appropriate.

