10.6.6. Treatment Month 6 (Visit T4; ± 5 days)

Patients will undergo the following assessments and procedures at Month 6 (Visit T4):

- Concomitant medication review (ongoing)
- Assess AEs, SAEs, and potential clinical endpoints (ongoing)
- Weight
- Vital signs
- Central clinical laboratory evaluations:
 - Hematology, blood chemistry, and urinalysis
 - Basic fasting lipids (TC, calculated LDL-C, HDL-C, non-HDL-C, and TGs) and hs-CRP
 - HbA_{1C}
- Return of IMP; assessment and recording of IMP adherence
- IWRS contact to obtain new MED ID numbers for double-blind IMP
- Dispense double-blind IMP (with amount sufficient until next clinic visit, typically 2 bottles) and provide dosing instruction
- Diet and exercise counselling
- Schedule next visit

Note: If the patient discontinues at any scheduled visit after T1, or between study visits, please proceed to Section 10.7 for detailed instructions.

The conduct of this visit may be altered to ensure patient safety during the global coronavirus disease of 2019 (COVID-19) pandemic. If permitted and approved by regional regulatory authorities and the appropriate IRB/IEC, this visit may be converted to a remote visit (telephone,

telemedicine, etc.) or conducted within the patient's home by a qualified visiting nurse. After obtaining either written or verbal consent from the patient, verifying the correct shipping address and patient availability to receive the shipment, IMP dispensation may be completed by utilizing an appropriate courier service. IMP may also be dispensed utilizing curbside pick-up at the site by the patient or patient representative. The procedures and data collected will be dependent upon the type of visit that is conducted. However, at a minimum, it is expected that the following data be collected regardless of whether the visit is conducted by phone or by visiting nurse: concomitant medications, assessment of AEs, SAEs, and clinical endpoints, and IMP adherence. When visits are conducted in the patient's home by a qualified visiting nurse, it is also expected, if logistically possible, that weight, vital signs, and samples for central laboratory evaluations will also be collected. Alterations to study visits and procedures during the pandemic will be recorded on a COVID-19-specific case report form.

Local laboratories may be utilized during the pandemic at the investigator's discretion with the following requirements:

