15.3.3. Secondary Efficacy Endpoint LDL-C

For this study, the directly measured LDL-C value is used when available, otherwise the calculated LDL-C value is used. All LDL-C analyses will be presented in both the conventional unit (mg/dL) and the standardized (SI) unit (mmol/L).

Percent change from baseline in LDL-C at Month 6 will be analyzed using a linear model with percent change from baseline as response, treatment group and baseline LDL-C as covariates. Since the variances of the response are potentially different for the two treatment groups (more variable with active treatment), the model will allow different residual variances by treatment group. Specifically, PROC MIXED can be used with ‘REPEATED / group = trt’ statement. In addition, Kenward-Roger method is to be used for approximating the degrees of freedom (‘DDFM=kenwardroger’ option to MODEL statement). Fitted mean (Least Square or LS means) percent changes from baseline for each treatment group will be calculated (with 95% CI) at baseline LDL-C level of 140 mg/dL. The estimated difference in percent changes from baseline between treatment groups will be provided with 95% CI and p-value for testing of no difference.

Since patients with missing LDL-C at Month 6 may have underlying distributions depending on whether the patient was assigned to the active treatment and remained on active treatment at the time, a pattern mixture model (PMM) is used for the analysis, using a multiple imputation approach. Specifically, missing LDL-C values at Month 6 were simulated using a linear regression model with Month 6 LDL-C value as response, and covariates including baseline LDL-C value, and an indicator variable that equals 1 if and only if the patient was assigned to the active treatment and remained on treatment at Month 6 (Day 182) (this can be achieved using PROC MI with monotone regression). Simulated datasets (20 replicates) are analyzed as described previously and the resulted estimates are combined using Rubin’s method (Rubin, 1987; PROC MIANALYZE).

For tertiary endpoints of LDL-C measured at all timepoints (Baseline, Month 3, 6, 12, 18, 24, 30, 36, 42, 48, 54, and 60), the observed values at each timepoint, changes from baseline, and percent changes from baseline will be summarized by treatment groups. Differences of the

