15.3.5. Secondary Efficacy Endpoint hs-CRP

Due to the highly skewed distribution of hs-CRP, a nonparametric analysis based on Wilcoxon rank sum test will be performed for percent change from baseline to Month 6. Hodges-Lehmann estimate of location shift and its 95% CI will be provided. Only observed values will be used with no imputation.

For hs-CRP measured at other timepoints (Month 12, and End-of-Study, which is defined to be the last measurement of each patient), the observed values at each timepoint, and percent changes from baseline will be summarized by treatment groups.

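### Month 6 hs-CRP is the only secondary biomarker endpoint with no analysis that handles missing values by drug status, and skewness does not justify the omission

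*Protocol*

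**What the plan says.** SAP 3.2.3 lists three secondary biomarker endpoints: LDL-C at Month 6, hs-CRP at Month 6, and HbA1c at Month 12 in inadequately controlled diabetes. Their missing data are handled as follows.

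- **hs-CRP, Protocol** (Synopsis, repeated in 15.7.2): Wilcoxon test and Hodges-Lehmann shift in the FAS, and "No imputation will be performed for the hs-CRP endpoint due to the extreme skewed distribution".
- **hs-CRP, SAP 15.3.5:** "Due to the highly skewed distribution of hs-CRP, a nonparametric analysis based on Wilcoxon rank sum test will be performed". It then adds: "Only observed values will be used with no imputation". Here skewness explains the test, and no separate reason is given for setting missing values aside.
- **LDL-C, SAP 15.3.3:** the reason for a pattern mixture model is given as "Since patients with missing LDL-C at Month 6 may have underlying distributions depending on whether the patient was assigned to the active treatment"; the same sentence also makes it depend on staying on drug. Missing values are multiply imputed (20 datasets) with two covariates: baseline LDL-C, plus "an indicator variable that equals 1 if and only if the patient was assigned to the active treatment and remained on treatment at Month 6".
- **HbA1c, SAP 15.3.4:** a pattern mixture model based on whether the patient was still on treatment at Month 12, like that for LDL-C.

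Protocol 15.7.2 makes the pattern mixture analysis primary and observed cases supportive for LDL-C and HbA1c.

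Protocol 10.6.6 puts both Month 6 markers on one line of the laboratory list: "Basic fasting lipids (TC, calculated LDL-C, HDL-C, non-HDL-C, and TGs) and hs-CRP". Protocol 10.6 also covers patients who stop drug and no longer attend: "If the patient agrees to telephone or other form of contact after withdrawing from IMP at any time after Visit T1". In that case sites gather what the patient reports, which does not include a blood sample. Protocol 10.7.3 offers similar alternatives.

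**The concern.** The FAS is all randomized patients, but a patient with no hs-CRP value in the Month 6 window contributes nothing to the hs-CRP analysis. The SAP recognises for LDL-C that such patients may differ by drug status, and models this. It does not do so for a marker drawn at the same visit. The two Month 6 results would be reported side by side as FAS effects while resting on different premises about missing data.

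The only stated reason is skewness. That is a reason to prefer ranks to means. It is not a reason to ignore missing data, because a skewed positive marker can be imputed as its logarithm.

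No other hs-CRP analysis in the available text fills the gap. SAP 15.4.2 drops values taken more than 7 days after the last dose, which moves further toward the on-drug effect. SAP 15.4.3 drops values after cross-in therapy, in the per-protocol set. Neither recovers an off-drug patient with no sample. At stake is whether the reported hs-CRP reduction describes all randomized patients or leans toward those still taking the drug.

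**Working it through.** **The plan's own figures.** The documents give no hs-CRP effect, standard deviation, sample size or missing rate, so there is no hs-CRP figure to reproduce. The powered figure is the primary event count: 4 × (1.960 + 1.282)² / (ln 0.85)² gives 1592 events against the stated 1620. That reproduces, but it has no bearing on hs-CRP.

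**Mechanism.** Let p be the share of active patients off drug at Month 6, and m_off and m_on the shares of off-drug and on-drug patients without a sample. The off-drug share among observed active patients is

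p(1 − m_off) / [p(1 − m_off) + (1 − p)(1 − m_on)].

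With p = 20% and m_on = 5%:

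- m_off = 5%: 0.190 / (0.190 + 0.760) = 20.0%. The mix is unchanged, so there is no lean.
- m_off = 30%: 0.140 / (0.140 + 0.760) = 15.6%.
- m_off = 70%: 0.060 / (0.060 + 0.760) = 7.3%.

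The lean therefore comes from unequal missingness, not from missingness as such.

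**Size on the planned estimator.** A simulation used 7000 patients per arm, 12 repeats per scenario and the Hodges-Lehmann shift in percent change. All hs-CRP inputs are assumptions: log-normal values, residual log SD 0.8, on-drug ratio 0.85 or 0.78, 5% to 20% off drug in each arm, 5% of on-drug patients missing, and off-drug active patients behaving like placebo. The last three columns show by how many percentage points observed cases overstate the reduction relative to complete FAS data.

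| On-drug ratio | Off drug | 5% of off-drug missing | 30% missing | 70% missing |
|---|---|---|---|---|
| 0.85 | 5% | 0.06 | 0.25 | 0.41 |
| 0.85 | 10% | −0.13 | 0.29 | 0.91 |
| 0.85 | 20% | 0.06 | 0.53 | 1.70 |
| 0.78 | 5% | 0.25 | 0.24 | 0.79 |
| 0.78 | 10% | −0.06 | 0.41 | 1.13 |
| 0.78 | 20% | 0.00 | 0.67 | 2.62 |

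The first results column is simulation noise, up to about 0.25 either way. The entries of 0.24 and 0.25 under 30% are no larger than that noise. In the worst case the estimates were −14.8 with complete data, −17.4 with observed cases and −18.3 on drug.

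A hand check of the worst case on the geometric mean scale agrees. The all-randomized ratio is 0.78^0.80 = 0.820. The observed-case ratio is 0.78^0.927 = 0.794. The difference is about 2.5 points.

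**Does skewness block imputation?** In the same simulation, log(hs-CRP) was imputed from baseline log(hs-CRP) and the LDL-C indicator (5 datasets), back-transformed, and summarised by Hodges-Lehmann. The result was within about 0.2 points of the complete-data estimate in 17 of 18 scenarios. The largest gap was 0.4, in the worst case (−15.2 against −14.8). This is favourable by construction, because off-drug active patients were simulated to behave as the imputation model assumes.

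**The case against.** A reader might infer four stronger things, none of which the documents support.

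1. *That the SAP itself says missing hs-CRP depends on drug status.* SAP 15.3.3 says only that it may, and only about LDL-C. The extension to hs-CRP is an inference from the visit schedule. The missing sets also overlap rather than coincide: in SAP Appendix 3 the Month 6 window is Day 2 to 273 for hs-CRP but Day 137 to 273 for lipids. An early or early-termination hs-CRP value can therefore count when LDL-C is missing. That recovers some patients, although such a value may reflect recent dosing.
2. *That the FAS hs-CRP result is in effect an on-drug result.* Protocol 10.6 has off-drug patients who attend clinic undergo every assessment except those concerning study drug. Their values stay in the analysis.
3. *That the direction is settled.* It requires off-drug active patients to be unsampled more often. The phone-contact option makes this plausible, but no rate is given. Protocol 10.6.6 also allows remote Month 6 visits during the pandemic, a route to missing samples not tied to drug status.
4. *That the overstatement is 1 to 3 points.* On-drug ratios of 0.75 to 0.80 with 5% to 15% of active patients both missing and off drug would give that: 0.80^0.95 = 0.809 and 0.75^0.85 = 0.783. But this treats every observed active patient as on drug. With 1% missing and off drug the shift is about 0.2 points (0.75^0.99 = 0.752).

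It is also fair to say that the observed-case method is prespecified and openly labelled, and that hs-CRP lies outside the seven-step hierarchy. SAP Sections 17 and 18 were not in the text available for this review, so a relevant analysis there cannot be excluded.

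These points limit the size and certainty of the concern. They do not supply a reason for treating hs-CRP differently from the other two biomarkers.

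**Conclusion.** The inconsistency is real and its stated reason is weak. The possible lean toward the on-drug effect is conditional: none if on-drug and off-drug patients are missing equally often, about 0.2 to 0.7 percentage points if 30% of off-drug patients are missing, and about 0.4 to 2.6 points if 70% are. These figures rest on the assumed effect, spread, discontinuation and missing rates listed in the working, none of which the documents provide. The consequence is confined to the estimate for one secondary biomarker with a nominal p-value. This is worth correcting because it is cheap, not because it threatens the trial's conclusions.

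**What to change.** In SAP 15.3.5:

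- Keep the Wilcoxon test and Hodges-Lehmann estimate on observed values, and describe them as an observed-case analysis.
- Add a prespecified analysis that imputes missing Month 6 log(hs-CRP) from baseline log(hs-CRP) and the on-active-drug indicator of Section 15.3.3, with 20 datasets. Back-transform, compute percent change, and obtain the Hodges-Lehmann shift in each dataset, with a standard error taken from its confidence interval (width / (2 × 1.96)). Combine by Rubin's method. The Wilcoxon p-value remains that of the observed-case analysis.
- Report Month 6 hs-CRP missingness by arm and by drug status, so that readers can judge whether the condition for a lean is met.

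The cost is SAP wording and reuse of the LDL-C imputation program. The analysis adds two assumptions: log-normality of the imputed values, and that off-drug active patients behave like placebo. The SAP already makes the second for LDL-C.

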3. LIST OF ABBREVIATIONS AND DEFINITIONS OF TERMS

The following abbreviations and specialist terms are used in this study protocol.

Table 1: Abbreviations and Specialist Terms

Abbreviation or Specialist Term	Explanation
ACL	adenosine triphosphate-citrate lyase
ACS	acyl-CoA synthetase
ACSVL1	very long-chain acyl-CoA synthetase 1
ADA	American Diabetes Association
ADR(s)	adverse drug reaction(s)
AE(s)	adverse event(s)
AESI	adverse events of special interest
Alb	albumin
ALK-P	alkaline phosphatase
ALT	alanine aminotransferase
ANCOVA	analysis of covariance
AST	aspartate aminotransferase
AU	Agatston units
AUC ₀₋₂₄	area under the curve during 24 hours
BMI	body mass index
BP	blood pressure
BUN	blood urea nitrogen
C5Research	Cleveland Clinic Coordinating Center for Clinical Research
Ca	calcium
CEC	Clinical Events Committee
CFR	Code of Federal Regulations
CI(s)	confidence interval(s)
CK	creatin kinase
COVID-19	Coronavirus disease of 2019
CPK	creatin phosphokinase
Cl	chloride
CNS	central nervous system
CoA	acetyl-coenzyme A
CO ₂	carbon dioxide
CRO(s)	contract research organization(s)
CTA	computed tomography angiography
CV	cardiovascular

Abbreviation or Specialist Term	Explanation
CVD	cardiovascular disease
CYP	cytochrome P450
DBP	diastolic blood pressure
DC	Diabetes Committee
DHA	docosahexaenoic acid
DMC	Data Monitoring Committee
EC	Executive Committee
ECG(s)	electrocardiogram(s)
eCRF	electronic case report form
EMA	European Medicines Agency
eGFR	estimated glomerular filtration rate
EPA	eicosapentaenoic acid
ESP15228	metabolite of bempedoic acid
EU	European Union
FAS	Full Analysis Set
FDA	US Food and Drug Administration
FSH	follicle-stimulating hormone
GCP	Good Clinical Practice
HbA _{1c}	glycosylated hemoglobin, Type A _{1c}
HBsAg	hepatitis B surface antigen
Hct	hematocrit
HCV	hepatitis C virus
HCV-Ab	hepatitis C antibodies
HDL-C	high-density lipoprotein cholesterol
Hgb	hemoglobin
H-L	Hodges-Lehmann
HMG-CoA	3-hydroxy-3-methylglutaryl coenzyme A
HR	hazard ratio
hs-CRP	high-sensitivity C-reactive protein
IB	Investigator's Brochure
ICD	Informed Consent Document
ICH	International Conference on Harmonisation
IEC	Independent Ethics Committee
IMP	investigational medicinal product
IND	Investigational New Drug Application
INR	international normalized ratio

Abbreviation or Specialist Term	Explanation
IRB	Institutional Review Board
ITT	intention-to-treat
IWRS	interactive web response system
K	potassium
K-M	Kaplan-Meier
LDH	lactate dehydrogenase
LDL-C	low-density lipoprotein cholesterol
LFT	liver function test
LS	least square
LSM	least squares mean
LTFU	lost-to-follow-up
MACE	major adverse cardiovascular event
MCH	mean corpuscular hemoglobin
MCHC	mean corpuscular hemoglobin concentration
MCV	mean corpuscular volume
MDRD	Modification of Diet in Renal Disease
MED ID	medication identification
MedDRA	Medical Dictionary for Regulatory Activities
MI	myocardial infarction
MMRM	mixed model repeated measure
MRI	magnetic resonance imaging
Na	sodium
NOAEL	no-observed-adverse-effect level
non-HDL-C	non-high-density lipoprotein cholesterol
NYHA	New York Heart Association
PAD	peripheral arterial disease
PCSK9	proprotein convertase subtilisin kexin type 9
PE	physical exam
PH	proportional hazards
PK	pharmacokinetic(s)
PMM	pattern mixture model
PT	prothrombin time
RBC	red blood cell
SAE(s)	serious adverse event(s)
SAP	Statistical Analysis Plan
SBP	systolic blood pressure

Abbreviation or Specialist Term	Explanation
SE	standard error
SGOT	serum glutamic oxaloacetic transaminase
SGPT	serum glutamic pyruvic transaminase
SI	statin intolerance
SmPC	Summary of Product Characteristics
SOC	System Organ Class
SOP(s)	standard operating procedure(s)
SP	Safety Population
SUSAR(s)	suspected and unexpected serious adverse reaction(s)
TB	total bilirubin
TC	total cholesterol
TEAE(s)	treatment-emergent adverse event(s)
TG(s)	triglyceride(s)
TIA(s)	transient ischemic attack(s)
TRAC	Tendon Rupture Adjudication Committee
TRIAC	Tendon Rupture Independent Adjudicator Charter
TSH	thyroid-stimulating hormone
ULN	upper limit of normal
US	United States
USPI	United States Prescribing Information
WBC	white blood cell
WHO	World Health Organization

